#### **Improvements in clinical impressions, as measured by CGI-I scores**

The proportion of subjects with a value of at least 2 (i.e., "Much improved" or better) on CGI-I will be analyzed using logistic regression applying the same model above described for CGI-S.

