4.6.1.10.9 Clinical Global Impression—Severity (CGI-S) and Improvement (CGI-I)

The CGI rating scales are tools used to evaluate both the severity of illness and change from baseline [39]. The CGI-S reflects the rater’s impression of the subject’s current autism severity on a 7-point scale ranging from no symptoms (1) to very severe symptoms (7). The CGI-I is used to assess the clinical change as compared to symptoms at baseline using a 7-point scale, ranging from very much improved (1) to very much worse (7). For this study modified versions will be used [40, 41].

Whenever possible, for any individual, these assessments should be done by the same rater throughout the study.

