### **2.1.2 Secondary Objectives**

The secondary objective of this study are as follows:

- To evaluate the efficacy of treatment with balovaptan 10 mg equivalent vs. placebo on:
  - Change from baseline on the Vineland™-II Composite standard score after 12 weeks and 24 weeks of treatment
  - Change from baseline in the Vineland™-II Communication, Socialization and Daily Living Skills domain standard scores after 12 weeks and 24 weeks of treatment
  - Proportion of subjects with ≥6-point improvement in the Vineland™-II 2DC score (clinically meaningful response)
  - Change from baseline in severity of clinical impressions as measured by CGI-S (Clinical Global Impressions-Severity) and OACIS-S (Ohio Autism Clinical Impressions Scale-Severity) after 12 weeks and 24 weeks of treatment
  - Improvements in clinical impressions as measured by CGI-I (Clinical Global Impressions-Improvement) and OACIS-I (Ohio Autism Clinical Impressions Scale-Improvement) after 12 weeks and 24 weeks of Treatment
  - Change from baseline in patient- or parent-reported Pediatric Quality of Life (PedsQL) v4.0 Generic Core Scale after 12 weeks and 24 weeks of treatment
  - Change from baseline in the Vineland™-II Composite standard score in adolescents and children independently after 12 weeks and 24 weeks of treatment
  - Change from baseline on the Vineland™-II 2DC score after 12 weeks of treatment
- To evaluate safety and tolerability of 24 and up to 76 weeks of treatment with balovaptan
- To evaluate the pharmacokinetics and exposure-response relationships of balovaptan and its metabolites, if appropriate

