#### **4.5 EFFICACY ANALYSES**

Summary tables and graphs will be provided both for the "Efficacy ITT Global" and for the "Efficacy ITT Inferential" populations, while listings of individual data will be provided for the "Efficacy ITT Global" population only, separately by subjects' patterns (b, c, d).

Inferential statistical analysis will be performed on pooled data from subjects taking balovaptan 10 mg equivalent dose compared with those from the concurrently randomized placebo in the corresponding randomization stage, as identified by the "Efficacy ITT Inferential" population. Multiple endpoints will be analyzed however, due to the exploratory nature of the study, multiplicity will not be statistically adjusted for and the risk of false positive results will be taken into consideration during the interpretation of the results.

The primary efficacy endpoint, the change from baseline of Vineland™-II 2-DC standard score, as well as the secondary endpoints expressed in terms of change from baseline on a continuous scale (namely, Vineland™-II standard scores, PedsQL Scale factors, ABC factors and RBS-R factors) will be analyzed using Mixed Model Repeat Measurements (MMRM) on the overall population of adolescents and children. The MMRM model will include treatment, sex and visit (week) as main effects, individual age and baseline score as covariates, and treatment-by-visit and baseline-by-visit as interaction terms. Visit will be fitted as a repeated effect with an unstructured correlation structure across visits within each subject. All main effects and interactions will be retained in the final model regardless of their statistical significance.

The results of the analysis will be presented as point estimates, 90% confidence intervals and associated p-values for the adjusted mean differences between 10 mg eq balovaptan and placebo after 24 weeks of treatment as well as at intermediate visits.

The main analysis outlined above will be done using a mixed effect model, which can handle missing data without any need to recur to imputation or discarding of data.

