The proportion of subjects with ≥6-point improvement in the Vineland™-II 2DC score (clinically meaningful response) will be analyzed using logistic regression. A Generalised Estimating Equations (GEE) model will be fitted including treatment, sex and visit (week) as main effects, age as covariate, baseline-by-visit and treatment-by-visit interactions, with subject fitted as a repeated effect. It will be based on the binomial distribution and thus the link function will be the 'logit'.

The odds ratio will be presented for descriptive purposes along with the corresponding 90% confidence interval and p-value for the comparisons between 10 mg eq balovaptan and placebo after 24 weeks of treatment as well as at intermediate visits.

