#### **Change from baseline in severity of clinical impressions as measured by CGI-S**

The proportion of subjects with at least 1-point decrease (i.e. improvement) from baseline on CGI-S will be analyzed using logistic regression. A GEE model will be fitted including treatment, sex and visit (week) as main effects, age and baseline CGI-S as covariates, baseline-by-visit and treatment-by-visit interactions, with subject fitted as a repeated effect. It will be based on the binomial distribution and thus the link function will be the 'logit'.

The odds ratio will be presented for descriptive purposes along with the corresponding 90% confidence interval and p-value for the comparisons between 10 mg eq balovaptan and placebo after 24 weeks of treatment as well as at intermediate visits.

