#### **4.5.1 Subgroup Analyses**

The results of the primary and secondary efficacy variables will be summarized within subgroups using descriptive statistics. The following categorization will be used to define the subgroups:

- Sex (male, female)
- Age (adolescents 13-17yrs, children 5-12yrs)

The statistical model for subgroup analyses of efficacy data will be performed using MMRM with subgroup, treatment-by-subgroup, subgroup-by-time and treatment-by-subgroup-by-time interaction terms included along the independent effects described above.

Estimates of treatment effect and associated 90% CIs will be presented in forest plots. Unadjusted p-values will also be presented for these analyses.

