#### **4.5.2 Interim Analysis**

The populations assessed at the Interim Analysis will be the “Safety Inferential” and the “Efficacy ITT Inferential” with all subjects randomized prior to 21FEB2019, which is the date of the last subject expected to provide 12 week data for the 10mg-Placebo comparison by 16MAY19.

The efficacy interim analysis will focus on the outcome measures derived from Vineland™-II and, only descriptively, from PedsQL v4.0 Generic Core Scale, CGI-I and CGI-S.

Summary statistics will be provided for the overall population and for the adolescents/ children subgroups separately.

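### SAP 4.5 states the CGI-I responder cut in the wrong direction: on a scale where 1 is best, at least 2 means scores 2 to 7, not the intended 1 or 2 (low severity)

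*SAP*

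**What the plan says.** The CGI-I paragraph of SAP 4.5 sets the analysis variable as "The proportion of subjects with a value of at least 2 (i.e., 'Much improved' or better) on CGI-I" and sends it to the same logistic model as CGI-S. Protocol 4.6.1.10.9 says that CGI-I is rated "using a 7-point scale, ranging from very much improved (1) to very much worse (7"), so lower is better.

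The CGI-S paragraph just before it in the SAP states its direction outright: "at least 1-point decrease (i.e. improvement) from baseline on CGI-S". For that model the SAP reports an odds ratio, labelled descriptive, with a 90% confidence interval and a p-value.

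The endpoint is a listed secondary objective in SAP 2.1.2, "Improvements in clinical impressions as measured by CGI-I (Clinical Global Impressions-Improvement"), with no numeric cut. SAP section 5 (Derived Endpoints) has no entry for CGI-I.

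**The concern.** The sentence holds two definitions of a responder that cannot both be programmed. The number, read as a number, excludes the best outcome and admits no change and every grade of worsening. The gloss says the opposite. This sentence is the only place in either document from which the CGI-I response variable can be built, so a programmer or an independent checker has nothing else to consult.

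If the number were followed, the analysis would in effect model the odds of not being very much improved. A drug that moved more subjects to score 1 would then show an odds ratio below 1. The same variable would carry into the subgroup work, since SAP 4.5.1 says that "The results of the primary and secondary efficacy variables will be summarized within subgroups using descriptive statistics".

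**Working it through.** **Step 1: which scores each rule selects.** The scale is 1 to 7, with 1 best and 7 worst (Protocol 4.6.1.10.9). The pairing of score 2 with *Much improved* is the SAP's own; the protocol labels only scores 1 and 7.

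| Rule | Responders | Non-responders |
|---|---|---|
| Number as written (≥ 2) | 2, 3, 4, 5, 6, 7 | 1 |
| Gloss (≤ 2) | 1, 2 | 3, 4, 5, 6, 7 |

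Both rules count score 2 as a response. They classify the other six scores oppositely.

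**Step 2: the odds ratio under the intended rule.** The documents give no CGI-I rates, so all rates here are assumptions. SAP 2.3 gives 80 evaluable subjects per arm. Take 35% active (28/80) and 25% placebo (20/80).

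- OR = (0.35/0.65) / (0.25/0.75) = 1.62
- SE of log OR = √(1/28 + 1/52 + 1/20 + 1/60) = 0.349
- 90% CI = exp(ln 1.615 ± 1.645 × 0.349) = 0.91 to 2.87

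**Step 3: the odds ratio under the literal rule.** Only score 1 is a non-response. With *p* the proportion scoring 1, the odds of response are (1 − *p*)/*p*. Take 5% of placebo subjects at score 1, so the placebo odds are 0.95/0.05 = 19.

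| Active at score 1 | Literal rate, active vs placebo | Odds, active | OR |
|---|---|---|---|
| 10% | 90% vs 95% | 9.00 | 0.47 |
| 7% | 93% vs 95% | 13.29 | 0.70 |
| 5% | 95% vs 95% | 19.00 | 1.00 |
| 4% | 96% vs 95% | 24.00 | 1.26 |

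For the first row (72/80 vs 76/80), the SE of log OR = √(1/72 + 1/8 + 1/76 + 1/4) = 0.634, and the 90% CI is 0.17 to 1.34.

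**Step 4: one full assumed distribution under both rules.** Scores 1 to 7 are active 5/25/35/30/3/1/1% and placebo 3/17/35/38/5/1/1%.

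- Gloss (≤ 2): 30% vs 20%, OR = (0.30/0.70)/(0.20/0.80) = 1.71
- Literal (≥ 2): 95% vs 97%, OR = (0.95/0.05)/(0.97/0.03) = 0.59

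The same data point in opposite directions. By construction, the literal odds ratio is below 1 whenever a larger share of active than placebo subjects score 1, whatever happens at score 2.

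**The case against.** The strongest reply is that the sentence explains itself. The words at least can be read as a degree of improvement rather than as arithmetic, and the named category leaves only one sensible coding, ≤ 2. A literal run would also give itself away: in the table above the response rates are 90% or more in both arms. This stands, and it is the main reason for the low rating.

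It is also fair that little rests on the endpoint. The SAP calls the study exploratory and makes no multiplicity adjustment. The odds ratio from the borrowed model is descriptive. At the interim, CGI-I is used "only descriptively, from PedsQL v4.0 Generic Core Scale, CGI-I and CGI-S". All of this stands too.

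The reply does not remove the contradiction. The gloss rescues the intent only for a reader who notices that the number disagrees with it.

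A reader might infer more: that the sponsor means to count worsening as response, or that the CGI-I result will be reversed. The documents support neither. The gloss shows the opposite intent. Reversal would need literal coding despite the gloss, together with an excess of score 1 on active. With fewer such subjects on active the literal odds ratio exceeds 1 (1.26 in the last row), and the interval for the 0.47 case includes 1.

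**Conclusion.** Wrong as written, with low practical severity. That the number contradicts the scale and its own gloss follows from the two documents alone and needs no assumption beyond the SAP's pairing of score 2 with *Much improved*. The possible effect, an odds ratio anywhere from 0.47 to 1.26 where the intended rule gives 1.62, rests wholly on assumed CGI-I rates and on the unlikely event of literal coding. It shows what the wording could do and does not forecast a result.

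Nor should the point be read as a threat to the trial's main conclusion. The primary endpoint is the change in Vineland-II 2DC at Week 24, and neither its analysis nor the sample size uses CGI-I.

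**What to change.** In the CGI-I paragraph of SAP 4.5, replace the phrase that sets the cut at a minimum value of 2 with: a score of 1 or 2 (≤ 2, i.e. *Much improved* or better). Make the change before database lock and check that the derivation program uses ≤ 2. The cost is a few words in the SAP. The intended analysis does not change, and no new data or modelling is needed.

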#### **4.5.1 Subgroup Analyses**

The results of the primary and secondary efficacy variables will be summarized within subgroups using descriptive statistics. The following categorization will be used to define the subgroups:

- Sex (male, female)
- Age (adolescents 13-17yrs, children 5-12yrs)

The statistical model for subgroup analyses of efficacy data will be performed using MMRM with subgroup, treatment-by-subgroup, subgroup-by-time and treatment-by-subgroup-by-time interaction terms included along the independent effects described above.

Estimates of treatment effect and associated 90% CIs will be presented in forest plots. Unadjusted p-values will also be presented for these analyses.

#### **4.5.2 Interim Analysis**

The populations assessed at the Interim Analysis will be the “Safety Inferential” and the “Efficacy ITT Inferential” with all subjects randomized prior to 21FEB2019, which is the date of the last subject expected to provide 12 week data for the 10mg-Placebo comparison by 16MAY19.

The efficacy interim analysis will focus on the outcome measures derived from Vineland™-II and, only descriptively, from PedsQL v4.0 Generic Core Scale, CGI-I and CGI-S.

Summary statistics will be provided for the overall population and for the adolescents/ children subgroups separately.

#### **4.5.3 PK/PD Analyses**

An exploratory graphical analysis of the relationship between pharmacokinetic exposure and efficacy will be performed by Clinical Pharmacology. For the exploratory graphical exposure-efficacy analyses,  $C_{ave}$  will be used either as a continuous covariate or as grouping variable. Graphical displays will include (but are not limited to) efficacy outcome measure vs. exposure by visit, and efficacy outcome measure vs. time, with trend lines split by exposure category (e.g. placebo, Low, Medium and High Tertile of  $C_{ave}$ ). The effect of subpopulations will also be investigated.

If warranted after review of initial graphical displays, a model based approach may be considered to quantify the exposure-effect relationship for Vineland™-II 2-DC. A model based exposure-efficacy analysis of other efficacy outcome measures might be considered upon agreement with the project team.

Results from pharmacometric analyses may be reported in a document separate from the clinical study report.

### **4.6 SAFETY ANALYSES**

Summary tables and graphs will be provided both for the “Safety Global” and for the “Safety Inferential” populations, while listings of individual data will be provided for the “Safety Global” population only, separately by subjects’ patterns (a, b, c, d).

As appropriate, listings, summary tables and graphs by treatment group will be provided for safety and tolerability assessments, including:

- Incidence of adverse events (overall, by intensity, and by relationship to study medication).

- Serious adverse events and adverse events of special interest will be reported separately.
- [REDACTED]
- Vital signs (systolic blood pressure, diastolic blood pressure, pulse rate, and orthostatic effects)
- [REDACTED]
- Physical examination (height, weight, neurological examination)
- Safety laboratory values (including hematology, blood chemistry, coagulation, and urinalysis parameters)
- Incidence of marked laboratory abnormalities
- Clinical assessment of suicidality (C-SSRS)

### **Adverse Events**

Verbatim descriptions of adverse events recorded on the eCRF by the Investigator during the study period will be mapped to the Medical Dictionary for Regulatory Activities (MedDRA) thesaurus terms. All adverse events will be tabulated by body system and preferred term for individual events within each body system. Adverse events will also be tabulated by severity and relationship to the study medication.

Serious adverse events will be summarized separately.

### **Clinical Laboratory**

Subjects' listings and summary statistics by treatment group at each assessment time will be presented using the International System of Units (SI units; *Système International d'Unités*). Laboratory data not reported in SI units will be converted to SI units before processing.

Laboratory test values will be presented by individual listings with flagging of values outside the normal ranges Roche standard reference ranges, rather than the reference ranges of the Investigator, will be used for all parameters. For most parameters the measured laboratory test result will be assessed directly using the Roche standard reference range. A transformation will be performed on some laboratory tests that lack sufficiently common procedures and have a wide range of Investigator ranges, e.g., enzyme tests that include AST, ALT, and alkaline phosphatase and total bilirubin. If the standard reference ranges for these parameters have a lower limit of zero only the upper limits of the ranges will be used in transforming the data.

For all laboratory parameters included, there exists a Roche predefined standard reference range. Laboratory values falling outside this standard reference range will be labeled "H" for high or "L" for low in study subject listings of laboratory data.

In addition to the standard reference range, a marked reference range has been predefined by Roche for each laboratory parameter. The marked reference range is broader than the standard reference range. Values falling outside the marked reference range that also

represent a defined change from baseline will be considered marked laboratory abnormalities (i.e., potentially clinically relevant). If a baseline value is not available for a subject, the midpoint of the standard reference range will be used as the subject's baseline value for the purposes of determining marked laboratory abnormalities. Marked laboratory abnormalities will be labeled in the subject listings as "HH" for very high or "LL" for very low.

### **Vital Signs and ECG**

Vital signs and ECG will be presented by individual listings and summary tables by treatment group and time of raw values and change from baseline.

### **Concomitant Medications**

Concomitant medications will be presented in summary tables and listings.

## **5 DERIVED ENDPOINTS**

### **• Aberrant Behavior Checklist (ABC)**

The ABC consists of 58 items subdivided in 5 subscales: Irritability, Lethargy and Social Withdrawal, Stereotypic Behavior, Hyperactivity/Non-Compliance and Inappropriate Speech.

The total scores for each of the 5 subscales (but not the values of all 58 items) will be electronically transferred to Roche.

### **• Pediatric Quality of Life Inventory (PedsQL™ 4.0) Generic Core**

The Pediatric Quality of Life Inventory PedsQL™4.0 Generic Core Scale assessment consists of 23 items encompassing 4 core scale domains:

- Physical Functioning (8 items)
- Emotional Functioning (5 items)
- Social Functioning (5 items)
- School Functioning (5 items)

summarised into:

- Total Score (23 items)

To create the scores for the above described 4 Functioning Scales and the Total Score a mean is computed as the sum of the items divided by the number of items answered (this accounts for missing data). If more than 50% of the items in the scale are missing, the Scale Score is not computed [Viecili and Weiss, 2015].

Additional Summary Scores will be derived as follows:

- Psychosocial Health Summary Score, as the sum of the items divided by the number of items (15, in case of no missing values) answered in the Emotional, Social, and School Functioning Scales.

- Physical Health Summary Score, which is the same as the Physical Functioning Scale Score.
- PedsQL Total Score, computed as the sum of all the items divided by the number of items (23, in case of no missing values) answered on all the Scales.

If more than 50% of the items are missing, the Summary Score is not computed [Viecili and Weiss, 2015].

The above described Functioning Scales and Summary Scores will be derived by Roche Statistical Programmer.

- **Pediatric Quality of Life Cognitive Functioning Scale**

The PedsQL Cognitive Functioning Scale consists of 6 items.

To create the Cognitive Functioning Total Score a mean is computed as the sum of the items divided by the number of items answered (this accounts for missing data). If more than 50% of the items in the scale are missing, the Scale Score is not computed [Viecili and Weiss, 2015].

- **Pediatric Quality of Life Family Impact Scale**

The Pediatric Quality of Life Inventory (PedsQL™) Family Impact Module version 2 consists of 36 items encompassing the following 6 scales

- Physical Functioning (6 items)
- Emotional Functioning (5 items)
- Social Functioning (4 items)
- Cognitive Functioning (5 items)
- Communication (3 items)
- Worry (5 items)

and the 2 following scales measuring parent-reported family functioning

- Daily Activities (3 items)
- Family Relationships (5 items)

The above described 6+2 scales are summarised by mean scores computed as the sum of the items scores divided by the number of items answered (this accounts for missing data). If more than 50% of the items in the scale are missing, the Scale Score is not computed [Varni et al., 2004].

Additional Summary Scores will be derived as follows:

- Total Score, by averaging across all 36 items
- Parent HRQoL Summary Score, by averaging the 20 items in Physical, Emotional, Social and Cognitive Functioning
- Family Summary Score, by averaging the 8 items in Daily Activities and Family Relationships

The above described Functioning Scale and Summary Scores will be derived by Roche Statistical Programmer.

- **Repetitive Behavior Scale - Revised (RBS-R)**

The RBS-R is a 43-item informant-based questionnaire assessing the variety of restricted and repetitive behaviors observed in individuals with ASD. The scale is grouped into 6 subscales: Stereotyped, Self-injurious, Compulsive, Ritualistic, Sameness, and Restricted Behaviors.

The subscales score will be electronically transferred to Roche.

- **Vineland™-II Adaptive Behaviour Scale (VABS)**

Values of Vineland™-II Adaptive Behavior Composite Score (as Sum and Standard score), domains (as v-scale and standard score for each of the 3 domains, Communication, Daily Living Skills, Socialization), subdomains (as raw and v-scale for each of the subdomains) and age-equivalent values (years:months, for each subdomain) will be derived via computerized system and electronically transferred to Roche.

The value for the primary endpoint, Vineland™-II Adaptive Behavior Scales 2-Domain Composite (2DC) Score, defined as the mean of the Communication domain standard score and the Socialization domain standard score, will be derived by Roche Statistical Programmer. If any of the two individual domain standard scores is missing the 2DC score is not computed.
